4.5.8.2 Treatment of Cetuximab Infusion Reactions

Treatment recommendations are provided below and may be modified based on local institutional standards, package inserts, and guidelines as appropriate.

Monitor participants for 1 hour following cetuximab infusions in a setting with resuscitation equipment and other agents necessary to treat anaphylaxis (eg, epinephrine, corticosteroids, intravenous antihistamines, bronchodilators, and oxygen). Monitor longer to confirm resolution of the event in participants requiring treatment for infusion reactions. Immediately and permanently discontinue cetuximab in participants with serious infusion reactions.

For **Grade 1** symptoms (Mild reaction; infusion interruption not indicated; intervention not indicated):

Remain at bedside and monitor participant until recovery from symptoms. Decrease the cetuximab infusion rate by 50% and monitor closely for any worsening. The total infusion time for cetuximab should not exceed 4 hours.

For **Grade 2** symptoms (Moderate reaction requires therapy or infusion interruption but responds promptly to symptomatic treatment [eg, antihistamines, non-steroidal anti-inflammatory drugs, narcotics, corticosteroids, bronchodilators, IV fluids]; prophylactic medications indicated for ≤ 24 hours):

Stop cetuximab infusion, administer bronchodilators, oxygen, etc. as medically indicated, and resume infusion at 50% of previous rate once allergic/hypersensitivity reaction has resolved or decreased to Grade 1 in severity, and monitor closely for any worsening.

For **Grade 3 or Grade 4** Symptoms (Severe reaction, Grade 3: prolonged [ie, not rapidly responsive to symptomatic medication and/or brief interruption of infusion]; recurrence of symptoms following initial improvement; hospitalization indicated for other clinical sequelae [eg, renal impairment, pulmonary infiltrates]). Grade 4: (life threatening; pressor or ventilatory support indicated)

Immediately discontinue infusion of cetuximab and disconnect participant from tubing. Begin an IV infusion of normal saline, and treat the participant as follows. Recommend bronchodilators, epinephrine 0.2 to 1 mg of a 1:1,000 solution for subcutaneous administration or 0.1 to 0.25 mg of a 1:10,000 solution and/or diphenhydramine 50 mg IV with methylprednisolone 100 mg IV (or equivalent), as needed. Participants have to be withdrawn immediately from the treatment and must not receive any further cetuximab treatment. Participant should be monitored until the investigator is comfortable that the symptoms will not recur. Cetuximab will be permanently discontinued.

Investigators should follow their institutional guidelines for the treatment of anaphylaxis. Remain at bedside and monitor participant until recovery from symptoms. In the case of late-occurring hypersensitivity symptoms (eg, appearance of a localized or generalized pruritus within 1 week after treatment), symptomatic treatment may be given (eg, oral antihistamine, or corticosteroids).

Once the cetuximab infusion rate has been decreased due to an allergic/hypersensitivity reaction, it will remain decreased for all subsequent infusions. If the participant has a second allergic/hypersensitivity reaction with the slower infusion rate, the infusion should be stopped and cetuximab treatment should be discontinued. If there is any question as to whether an observed reaction is an allergic/hypersensitivity reaction of Grade 1 - 4, the sponsor should be contacted immediately to discuss and grade the reaction.

4.6 Blinding/Unblinding

Not applicable.

4.7 Treatment Compliance

Treatment compliance will be monitored by drug accountability as well as the participant's medical record and eCRF.

4.8 Destruction of Study Drug

For this study, study drugs (those supplied by BMS or sourced by the investigator) such as partially used study drug containers, vials and syringes may be destroyed on site.

Any unused study drugs can only be destroyed after being inspected and reconciled by the responsible Study Monitor unless study drug containers must be immediately destroyed as required for safety, or to meet local regulations (eg, cytotoxics or biologics).

On-site destruction is allowed provided the following minimal standards are met:

- On-site disposal practices must not expose humans to risks from the drug.
- On-site disposal practices and procedures are in agreement with applicable laws and regulations, including any special requirements for controlled or hazardous substances.
- Written procedures for on-site disposal are available and followed. The procedures must be filed with the site's SOPs and a copy provided to BMS upon request.
- Records are maintained that allow for traceability of each container, including the date disposed of, quantity disposed, and identification of the person disposing the containers. The method of disposal, ie, incinerator, licensed sanitary landfill, or licensed waste disposal vendor must be documented.
- Accountability and disposal records are complete, up-to-date, and available for the Monitor to review throughout the clinical trial period.

If conditions for destruction cannot be met the responsible Study Monitor will make arrangements for return of study drug.

It is the investigator's responsibility to arrange for disposal of all empty containers, provided that procedures for proper disposal have been established according to applicable federal, state, local, and institutional guidelines and procedures, and provided that appropriate records of disposal are kept.

4.9 Return of Study Drug

If study drug will not be destroyed upon completion or termination of the study, all unused and/or partially used study drug that was supplied by BMS must be returned to BMS. The return of study drug will be arranged by the responsible Study Monitor.

It is the investigator's responsibility to arrange for disposal of all empty containers, provided that procedures for proper disposal have been established according to applicable federal, state, local, and institutional guidelines and procedures, and provided that appropriate records of disposal are kept.

Arrangements for the return of study drug will be made by the responsible Study Monitor.

4.10 Retained Samples for Bioavailability / Bioequivalence

Not Applicable

5 STUDY ASSESSMENTS AND PROCEDURES

5.1 Flow Chart/Time and Events Schedule

Table 5.1-1: Screening Procedural Outline (CA209651)

Procedure	Screening Visit	Notes
Eligibility Assessments		
Informed Consent	X	Original IC before start of screening procedures for protocol participation; Study allows for re-enrollment of a participant that has discontinued the study as a pre-treatment failure. If re-enrolled, the participant must be re-consented and assigned a new participant number from IVRS.
Inclusion/Exclusion Criteria	X	All inclusion/exclusion criteria should be assessed at screening and confirmed prior to first dose
Medical History	X	
Tumor Tissue Sample	X	Tumor sample prior to therapy is mandatory for PD-L1 testing (sample to be shipped to Central Lab) and for HPV p-16 testing for participants with oropharyngeal CA (sample either tested locally or shipped to Central Lab). If a recent tumor sample (obtained within 6 months of enrollment) is not available at screening, a fresh biopsy will be taken at any point prior to randomization. Sufficient tumor tissue should be submitted either 2 full block or a minimum of 25 slides, obtained from core biopsy, punch biopsy, excisional biopsy or surgical specimen). Contact the Study Director if sufficient tissue is not available.
Screening/Baseline Tumor Assessment	X	Must be performed within 28 days prior to first dose. CT with IV contrast of Neck, Chest, Abdomen, Pelvis (CAP) and all other known sites of disease should be imaged during the screening period. Gadolinium contrast enhanced MRI of the neck and CAP may be obtained if CT iodinated contrast is contraindicated. MRI of brain without and with Gadolinium is required for ALL participants in screening to rule out brain metastases. Note: MRI of the brain is preferred but CT scan is acceptable. CT of the head (with and without contrast) to be performed if MRI is contraindicated or unavailable. TAs following RECIST 1.1 criteria.

Table 5.1-1: Screening Procedural Outline (CA209651)

Procedure	Screening Visit	Notes
Prior Medications	X	Dates and doses of platinum-based therapy plus prior medications subjects received to treat cancer.
ECOG Performance Status	X	During screening; within 28 days prior to the first dose.
Safety Assessments		
Vital Signs	X	Including BP, HR, and temperature. Obtain vital signs at the screening visit and within 72 hours prior to first dose.
Physical Measurements/Physical Examination	X	Height and Weight. BSA. Within 28 days prior to first dose
12 lead ECG		12 Lead ECG Required at Screening, See Section 5.3.4
Assessment of Signs and Symptoms	X	Within 14 days prior to first dose
Concomitant Medication Collection	X	Within 14 days prior to first dose
Adverse Events Assessment	X	
Laboratory Tests	X	
CBC w/differential, Chemistry panel including: Albumin, LDH, AST, ALT, ALP, T.Bili, BUN or serum urea level, creatinine, Ca, Mg, Na, K, Cl, phosphate, glucose, amylase, lipase, TSH, Free T4, Free T3. Within 14 days prior to randomization and again within 72 hours prior to first dose.
 
Hepatitis B surface antigen (HBV sAg), and hepatitis C antibody (HCV Ab) or Hepatitis C RNA (HCV RNA). Within 28 days prior to first dose.
 
Participants who test positive for hepatitis C but have undetectable HCV RNA are allowed to enroll.

Pregnancy Test (WOCBP only)	X	Serum or urine within 24 hours of first dose.

Table 5.1-1: Screening Procedural Outline (CA209651)

Procedure	Screening Visit	Notes
Biomarker Assessments		
Tumor Biopsy sample:	X	See Table 5.6-1 and above.
Study Drug		
Enrollment In IVRS	X	

Table 5.1-2: On Treatment Procedural Outline (All Treatments) CA209651 (All Cohorts)

Procedure	During Treatment Visit ^{a,b}	Notes
Safety Assessments		
Targeted Physical Examination	X	
Vital Signs	X	Including BP, HR, and temperature prior to dosing for all treatment Arms.
Physical Measurements (including performance status)	X	Weight and ECOG status within 72 hours prior to each dose. The dosing calculations should be based on the body weight. If the participant's weight on the day of dosing differs by > 10% from the weight used to calculate the dose, the dose must be recalculated. All doses should be rounded to the nearest milligram.
Adverse Events Assessment	X	
Laboratory Tests	X	Arm A: On-study local laboratory assessments should be done within 72 hours prior to each dose. For Arm B: Within 72 hours prior to dosing of Day 1 of each Cycle, and every 3 weeks or more frequently as clinically indicated for weekly cetuximab dosing visits). CBC w/differential, (albumin if clinically indicated), LFTs (ALT, AST, total bilirubin, alkaline phosphatase), BUN or serum urea level, creatinine, Ca, Mg, Na, K, Cl, LDH, phosphate, glucose, amylase, lipase, TSH with reflexive Free T4, Free T3 (ONLY if TSH is abnormal). (Thyroid Function Testing to be evaluated every 6 weeks).
Pregnancy Test (WOCBP only)	X	Serum or urine within 24 hours prior to first dose and then every 4 weeks (\pm 1 week) regardless of dosing schedule.
Concomitant Medications	X	
Efficacy Assessments		
Tumor Assessment	X	
 • Tumor assessments should occur every 6 weeks (starting from first dose \pm 1 week) for the first 48 weeks, then every 12 weeks (\pm 1 week) until disease progression or treatment is discontinued, whichever occurs later. If treatment beyond progression is approved, then scanning should continue every 6 weeks \pm 1 week until further progression is determined. • CT or MRI of the neck, chest, abdomen, pelvis and all known sites of disease. Use same imaging method as was used at screening/baseline.

Table 5.1-2: On Treatment Procedural Outline (All Treatments) CA209651 (All Cohorts)

Procedure	During Treatment Visit ^{a,b}	Notes
		
 MRI of the brain (without AND with Gadolinium contrast) is required for participants with a history of brain metastasis. Note: MRI of the brain is preferred but CT scan is a participant acceptable. 
Surveillance scans should be performed approximately every 12 weeks, or sooner if clinically indicated. (CT of the head without AND with contrast may be performed if MRI is contraindicated).

Outcomes Research Assessment		
FACT-H&N	X	
Assessed following randomization but before treatment every 6 weeks (\pm 1 week) regardless of dosing.
 
Can be collected over the phone at regularly scheduled time if needed.

EQ-5D-3L	X	
Assessed following randomization but before treatment every 6 weeks (\pm 1 week) regardless of dosing.
 
Can be collected over the phone at regularly scheduled time if needed.

Health care resource utilization questions	X	To be completed by the site in CRF
Pharmacokinetic Assessments		
PK samples (Arm A Only)	X	See Table 5.5-1.
Immunogenicity blood samples	X	See Table 5.5-1.
Biomarker Assessments		
Serum sample: Soluble Biomarkers	X	See Table 5.6-1.
Whole Blood sample: SNP (pre dose D1 only) & Gene expression	X	See Table 5.6-1
Plasma samples	X	See Table 5.6-1
Tumor Biopsy Sample:	X	
Tumor biopsy specimens will be obtained from consenting participants within all treatment arms at Week 7 and once disease progression has been documented (See Table 5.6-1). Biopsy should be excisional, incisional or core needle (fine needle aspiration is insufficient) and submitted to central lab see also Table 5.6-1

Table 5.1-2: On Treatment Procedural Outline (All Treatments) CA209651 (All Cohorts)

Procedure	During Treatment Visit ^{a,b}	Notes
Saliva Sample: Oral microbiome	X	See Table 5.6-1
Clinical Drug Supplies		
IVRS Drug Vial Assignment	X	
Dispense Study Drug	X	Within 3 days from randomization, the participant must receive the first dose of study medication.

^a For Ipilimumab/Nivolumab Arm: Visits occur every 2 weeks

^b For EXTREME regimen Arm: Visits occur every 3 weeks

Table 5.1-3: Follow-Up Period (all treatment groups)

Procedure	Follow Up, Visits 1 and 2 ^a	Survival Follow-Up Visits ^b	Notes
Safety Assessments			
Targeted Physical Examination	X		To assess for potential late emergent study drug related issues.
Vital Signs	X		
Adverse Events Assessment	X		In survival period only to include toxicities from study therapy.
Review of Concomitant Medication	X	X	Document Subsequent Cancer Therapy
Laboratory Tests	X		CBC w/ differential, LFTs, BUN or serum urea level, creatinine, Ca, Mg, Na, K, Cl, LDH, phosphate, glucose, amylase, lipase. TSH (+ reflex Free T4 and Free T3 collected ONLY if TSH is abnormal). To be done at FU1, to be repeated at FU2, if study related toxicity persists.
Pregnancy Test (WOCBP only)	X		Serum or urine.
Efficacy Assessments			
Tumor Assessment	X	X	Only for participants without progression. - Tumor assessments should occur every 6 weeks (\pm 1 week) for the first 48 weeks, then every 12 weeks (\pm 1 week) until disease progression or treatment is discontinued (whichever occurs later). - CT or MRI of the neck, chest, abdomen, pelvis and all known sites of disease. Use same imaging method as was used at screening/baseline. - MRI of the brain (without AND with Gadolinium contrast) is required for participants with a history of brain metastasis. Note: MRI of the brain is preferred but CT scan is acceptable. Surveillance scans should be performed approximately every 12 weeks, or sooner if clinically indicated. (CT of the head without AND with contrast may be performed if MRI is contraindicated).
Outcomes Research Assessment			
FACT-H&N	X		Can be collected over the phone.
FHNSI-10		X	Can be collected over the phone.

Table 5.1-3: Follow-Up Period (all treatment groups)

Procedure	Follow Up, Visits 1 and 2 ^a	Survival Follow-Up Visits ^b	Notes
EQ-5D-3L	X	X	Can be collected over the phone.
Health care resource utilization questions	X		To be completed by the site in CRF
Participant Status			
Survival Status	X	X	Every 3 months after FU 2; may be accomplished by visit, phone contact or email, to include assessment of subsequent anti-cancer therapy

^a Follow Up visits 1 (FU1) and 2 (FU2) are in clinic visits. Follow-up visit 1 (FU1) = 30 days from the last dose ± 7 days or coincides with the date of discontinuation (± 7 days) if date of discontinuation is greater than 35 days after last dose, Follow-up visit 2 (FU2) = 90 days (± 7 days) from Follow-up Visit 1

^b Survival Follow Up Visits may be conducted in clinic or via telephone contact: Every 3 Months (± 7 days) from FU2

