Participants will be stratified on tumor cell PD-L1 status (expressing vs non-expressing or non-evaluable. Up to 10% of randomized subjects can be included into the study as non-evaluable. After this point, subjects with non-evaluable results will not be permitted to be randomized; the site would need to submit an additional tumor tissue for testing with either a result of expressing or non-expressing in order to randomize the subject).

- Participants must have the result of tumor cell PD-L1 IHC testing from the Central Lab available (and HPV p-16 result if not available locally) in order to randomize into the study.
- Participant is assessed for study eligibility.
- All screening assessments and procedures must be performed prior to randomization.

Treatment Phase

- The treatment begins with the contact to the IVRS to randomize the patient.
- Treatment to begin within 3 days of randomization.

Arm A: Nivolumab + Ipilimumab Combo (1 Cycle = 6 Weeks):

- Nivolumab 3 mg/kg IV will be administered every 2 weeks (\pm 3 days) + Ipilimumab 1 mg/kg IV will be administered every 6 weeks (\pm 3 days).
- On the day of infusion, nivolumab is to be administered first. The second infusion will always be ipilimumab and will start at least 30 minutes after completion of the nivolumab infusion.
- Nivolumab 3 mg/kg Q2W and ipilimumab 1 mg/kg Q6W will be continued until the progression of disease, discontinuation due to toxicity, withdrawal of consent, or a maximum of 24 months from the first study treatment, or study closure (see [Section 3.5](#) for full list of treatment discontinuation reasons). Participants may discontinue only ipilimumab and continue treatment with nivolumab if certain circumstances are met (See [Section 4.5.6](#), Treatment Beyond Disease Progression (Arm A only).
- Treatment beyond initial investigator-assessed RECIST 1.1-defined progression is permitted for Arm A if the participant has investigator-assessed clinical benefit and is tolerating treatment.

Arm B: EXTREME regimen Arm (1 Cycle = 3 weeks):

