5.7 Outcomes Research Assessments

The evaluation of health-related quality of life is an increasingly important aspect of clinical efficacy in oncology trials. Such data provide an understanding of the impact of treatment from the patient's perspective and offer insights into patient experience that may not be captured through physician reporting. Additionally, generic health-related quality of life measures provide data needed for calculating utility values to inform health economic models.

Participants will be asked to complete the EQ-5D-3L and FACT-H&N before any clinical activities are performed during on-study clinic visits and at follow up visits 1 and 2. In addition, the EQ-5D and FHNSI-10 will be completed at designated time points during the survival follow-up phase. The questionnaires will be provided in the participant's preferred language if available and may be administered by telephone during the survival follow-up phase. A standardized script will be used to facilitate telephone administration of the EQ-5D. A similar script does not exist for the FHNSI-10, though participants will be provided with a hard copy of the questionnaire to take home and use as a visual aid during telephone interviews. Participants not able to vocalize responses over the phone will be afforded the opportunity to complete the questionnaires by pen and paper (initialing and dating each page) and return them by mail to the study site. [Table 5.1-2](#) and [Table 5.1-3](#) provide information regarding the timing of participant-reported outcomes assessments.

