8.4.6 Outcomes Research Analyses

Exploratory analyses of EQ-5D and FACT-H&N (including FHNSI-10) data will be performed in randomized participants who have an assessment at baseline (Day 1, assessment prior to administration of drug on day of first dose) and at least 1 subsequent assessment while on treatment. Questionnaire completion rate, defined as the proportion of questionnaires actually received out of the expected number, will be calculated and summarized at each assessment point.

EQ-5D data will be described by treatment group as randomized in the following ways:

- EQ-5D index scores and post-baseline changes in scores will be summarized at each assessment time point using descriptive statistics (ie, N, mean with SD and 95% CI, median, first and third quartiles, minimum, maximum). In the base case, scores will be calculated using the UK preference-weighting algorithm.

- EQ-5D VAS scores and post-baseline changes in scores will be summarized at each assessment time point using descriptive statistics (ie, N, mean with SD and 95% CI, median, first and third quartiles, minimum, maximum).
- The proportion (N) of participants reporting no, moderate, or extreme problems will be presented for each of the 5 EQ-5D dimensions at each assessment time point. Participants with missing data will be excluded from the analysis.
- A by-participant listing of the level of problems in each dimension, corresponding EQ-5D health state (ie, 5-digit vector), EQ-5D index score, and EQ-5D VAS score will be provided.

FACT-H&N data collected during on-study clinic visits and at follow up visits 1 and 2 will be described by treatment group as randomized in the following ways:

- Scores and post-baseline changes in scores for the following components of the FACT-H&N will be summarized at each assessment time point using descriptive statistics (ie, N, mean with SD and 95% CI, median, first and third quartiles, minimum, maximum): FACT-G, PWB, SWB, EWB, FWB, HNC, FHNSI-10, FACT-H&N TOI, FACT-H&N total, and individual FACT-H&N items.

FHNSI-10 data will be described by treatment group as randomized in the following ways:

- Scores and post-baseline changes in scores will be summarized at each assessment time point (i.e., first, second, third, etc. survival follow-up visit recognizing that the timing of visits will vary among participants) using descriptive statistics (ie, N, mean with SD and 95% CI, median, first and third quartiles, minimum, maximum).

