#### 2.3 Blinding and Unblinding

This is an open label study. However, the sponsor is strictly prohibited from looking at unblinded aggregate efficacy data while the study is still ongoing. The sponsor is forbidden from looking at data by arm while the study is ongoing.

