#### 4.3.5 EuroQoL EQ-5D-3L

Subjects' reports of general health status will be assessed using the EuroQoL Group's EQ-5D-3L. EQ-5D-3L essentially has 2 components: the descriptive system and the visual analogue scale (VAS).

The instrument's descriptive system consists of 5 dimensions: mobility, self-care, usual activities, pain/discomfort, and anxiety/depression. Each dimension has 3 levels, reflecting "no health problems," "moderate health problems," and "extreme health problems." A dimension for which there are no problems is said to be at level 1, while a dimension for which there are extreme problems is said to be at level 3. Thus, the vectors 11111 and 33333 represent the best health state and the worst health state, respectively, described by the EQ-5D-3L. Altogether, the instrument describes  $3^5 = 243$  health states. Empirically derived weights can be applied to an individual's responses to the EQ-5D-3L descriptive system to generate an index measuring the value to society of his or her current health. Such preference-weighting systems have been developed for the UK, US, Spain, Germany, and numerous other populations. For this study, EQ-5D-3L utility index values will be computed using a scoring algorithm based on the United Kingdom Time-Trade-Off (UK TTO) value set.

In addition, the EQ-5D-3L includes a VAS, which allows respondents to rate their own current health on a 101-point scale ranging from 0="worst imaginable" health to 100="best imaginable" health state.

A change from baseline of 0.08 for the EQ-5D-3L utility index score and of 7 for the EQ-5D-3L VAS are considered minimally important differences for the EQ-5D-3L.

All questionnaires completed at baseline and on-study will be assigned to a time-point according to the windowing criteria in Table 4.3.5-1 and included in the analysis. In case a subject has two on-study assessments within the same window, the assessment closest to the time-point will be used. And, in the case of two assessments at a similar distance to the time-point, the latest one will be chosen. In the event where the subject has no assessment at all in a specific window, the observation will be treated as missing for that time-point.

Table 4.3.5-1: Time Windows for EQ-5D and FACT-HN (FHNSI-10)

Nominal Time-Point	Time Window
Week 1 (Baseline)	≤ Date of first dose of study therapy
On-Treatment: (until last dose date)	
Week 7 (Day 43)	Day 2 - ≤ Day 64

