#### 4.3.7 Time to Disease-related Symptom Deterioration

Time to disease-related symptom deterioration (TTSD) is defined as the time from randomization to a clinically meaningful decline from baseline FHNSI-10 score (worsening from baseline  $\geq 3$  points).

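### In this open-label trial the baseline FACT-H&N and EQ-5D-3L are scheduled after randomization, so the reference value for the exploratory patient-reported analyses is exposed to knowledge of the arm

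*Protocol*

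**What the plan says.** Protocol 3.1 separates the phases at randomization. For screening it says "All screening assessments and procedures must be performed prior to randomization", and for the treatment phase "The treatment begins with the contact to the IVRS to randomize the patient". Table 5.1-1, the screening schedule, lists no FACT-H&N or EQ-5D-3L.

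Both questionnaires first appear in Table 5.1-2, the on-treatment schedule, with the timing "Assessed following randomization but before treatment every 6 weeks". Table 5.1-2 also requires the first dose within 3 days of randomization.

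Protocol 8.4.6 restricts the patient-reported analyses to randomized participants with an "assessment at baseline (Day 1, assessment prior to administration of drug on day of first dose") and a later on-treatment assessment. SAP Table 4.3.5-1 sets the baseline window as "≤ Date of first dose of study therapy". SAP 4.3.7 defines TTSD as the "time from randomization to a clinically meaningful decline from baseline FHNSI-10 score", the decline being 3 points or more.

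On blinding, SAP 2.3 states "This is an open label study", and protocol 4.6 treats blinding as not relevant to this trial.

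**The concern.** A baseline is useful as a reference because assignment cannot have influenced it. Here it is collected after assignment in an unblinded trial that compares immunotherapy with platinum, fluorouracil and cetuximab. The content is subjective: EQ-5D-3L has an anxiety/depression item, and FHNSI-10 draws on emotional and functional well-being items as well as symptoms (protocol 5.7). Relief or disappointment at the allocation could move the answers, and differently in the two arms.

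Every EQ-5D and FACT-H&N change score, the proportion deteriorated and TTSD is measured against this value. If the arms differ at baseline, the reader cannot tell chance imbalance from a reaction to allocation. TTSD is a named objective in each arm, and protocol 5.7 gives informing health economic models as a purpose of the utility data, so these summaries will be read comparatively even though no test is planned.

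**Working it through.** No sample size, power, alpha or event count depends on this point, so there is no figure in the plan to reproduce. The check is a comparison of the timing statements.

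1. **Is a form scheduled before randomization?** No. Table 5.1-1 has none, and Table 5.1-2 starts both after randomization.
2. **Does any other text move it earlier?** Protocol 5.7 says "Participants will be asked to complete the EQ-5D-3L and FACT-H&N before any clinical activities are performed during on-study clinic visits". That orders tasks within a visit and does not place the form before the randomization call.
3. **Does the SAP window help?** The window in SAP Table 4.3.5-1 would accept a form completed before randomization, but no scheduled visit produces one.
4. **Do participants know their arm by then?** This is inference. The trial is open label, the treatment phase opens with the randomization call, and the form is due on the day of first dose or in the preceding gap of at most 3 days. Knowledge of the arm is the natural reading, but no section says when a participant is told.
5. **Which analyses use this value?** FHNSI-10 is scored from FACT-H&N items, so it shares the same baseline. The affected outputs are the change scores and deterioration summaries in protocol 8.4.6 and SAP 7.9.1 and 7.9.2. All are descriptive: means, proportions, and Kaplan-Meier medians with confidence intervals.

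**How a shift would act.** Let *b* be the shift in the baseline report caused by knowing the arm, and *f* the shift in a later report. Then

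observed decline = true decline + (*b* − *f*).

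With a baseline taken before randomization, *b* = 0 and the error is −*f*.

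FHNSI-10 has 10 items scored 0 to 4, so its range is 0 to 40, and the event is a decline of at least 3. The documents give no SD and no expected baseline difference. Taking shifts between −1 and +1 point purely as an assumption:

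| Assumed shift | Current schedule | Baseline before randomization |
|---|---|---|
| *b* = +1, *f* = 0 | true fall of 2 reads as 3 (event) | no error |
| *b* = −1, *f* = 0 | true fall of 3 reads as 2 (no event) | no error |
| *b* = *f* = +1 | shifts cancel | true fall of 3 reads as 2 |
| *b* = *f* = −1 | shifts cancel | true fall of 2 reads as 3 |

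The effect therefore depends on whether the reaction to allocation fades or persists, and the documents do not settle that.

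**The case against.** The strongest reply is that every later form is also answered with knowledge of the arm. If the reaction persists, it cancels in change scores under the current schedule and would not cancel after the proposed move. That stands as a limit on size: the change protects the reference value only and is not shown to reduce total bias in every case. It does not make a baseline taken after allocation preferable, because only a form completed before allocation is free of it by design.

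It also stands that these objectives are exploratory, that no between-arm test, hazard ratio or baseline-adjusted model is planned for them, and that under protocol 8.3.3 death counts as deterioration whatever the baseline score.

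A reader might infer several stronger points that the documents do not support:

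- **A baseline shift carries in full into every visit's mean change.** This holds only if the shift is confined to baseline (*f* = 0).
- **The timing removes never-dosed participants and those who leave on learning their arm.** Protocol 8.4.6 requires a later assessment on treatment. SAP 7.9 requires a post-baseline assessment, and the SAP follow-up windows hang on last dose or discontinuation. These participants stay out wherever baseline is placed.
- **TTSD is distorted because its clock starts before its baseline.** The gap is at most 3 days against assessments 6 weeks (42 days) apart, and no score-based event can occur within it.
- **A repeat analysis without post-randomization baselines would settle the matter.** Under the current schedule that would exclude nearly everyone.

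**Conclusion.** The point holds as a modest design weakness. The documents are explicit that the first questionnaires follow randomization and that the trial is open label. That participants know their arm when they answer is a probable inference. The result is exposure of the patient-reported reference value to avoidable bias. The documents do not show that bias occurred, and they give no basis for its size or direction; the 1-point figures above are illustrations.

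A reader might conclude that the patient-reported results are invalid or that the trial's main conclusions are at risk. Neither follows. The affected summaries are exploratory and descriptive, and OS and BICR-based PFS, ORR and DOR do not use these forms. The change is worth making because it is cheap and the documents give no reason for the present timing.

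**What to change.** **Schedule.** Add FACT-H&N and EQ-5D-3L to Table 5.1-1, completed after consent and before the IVRS randomization call. Remove the post-randomization baseline administration from Table 5.1-2. Record that the form preceded the call, since both may fall on the same date.

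**Definition.** In protocol 8.4.6 and SAP Table 4.3.5-1, define baseline as the last questionnaire on or before randomization. Where none exists, use a form completed after randomization but before dosing, and flag it.

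**Participants already randomized.** Keep the pre-dose form as baseline, report baseline scores and baseline completion by arm, and state in the report that these baselines were collected after open-label allocation.

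**Cost.** One schedule row and two wording changes, with no new instrument. A few forms will come from people who are then not randomized. The form may also precede first dose by more than the present 3 days. If it were collected with the screening laboratory tests, which Table 5.1-1 allows up to 14 days before randomization, the gap could reach 14 + 3 = 17 days, so it is better completed close to the call.
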